1. INTRODUCTION

TOZ-CL06 is a 52-week open-label study in levodopa-treated patients with PD experiencing end-of-dose “wearing-off”. This statistical analysis plan (SAP) describes the statistical methods to be used during the reporting and analyses of data collected in TOZ-CL06.

This SAP should be read in conjunction with the study protocol. This plan is developed using the protocol version 2.0 dated 03-FEB-2017.

2. STUDY OBJECTIVES

2.1. Primary Objectives

To evaluate the safety and tolerability of tozadenant in levodopa-treated PD patients experiencing motor fluctuations, based on assessment of treatment-emergent adverse events (TEAEs), vital signs, electrocardiograms (ECGs), and clinical laboratory tests.

2.2. Secondary Objectives

To evaluate the effects of tozadenant on the occurrence of daytime drowsiness, impulsive behavior, and suicidality.

3. STUDY DESIGN

This is a Phase 3, international, multicenter, open-label study in levodopa-treated patients with PD experiencing end-of-dose “wearing-off”. This study includes a Screening Period of up to 6 weeks that starts with a Screening Visit, followed by a 52-week Open-Label Treatment Period and a Safety Follow-Up Visit 4 weeks after completion of investigational treatment. After providing written informed consent, patients will undergo screening evaluations. Patients must meet all inclusion criteria and none of the exclusion criteria and they must successfully complete the diary training and achieve 80% overall diary concordance with the PD diary trainer/rater including at least 1 OFF interval to be considered for enrollment. If preliminary eligibility is confirmed by the investigator, patients will then be scheduled for a Baseline Visit and will be required to return a valid set of Baseline diaries. Final eligibility will be determined at the Baseline Visit.

Patients will return to the study site for evaluation at scheduled visits at Weeks 2, 6, 12, 24, 36, and 52. Patients will be contacted by telephone before the start of each 3-day PD diary completion period to be reminded to complete the diary. A final Safety Follow-Up Visit (Week 56) will occur 28 ± 3 days after the patient’s last open-label dose of tozadenant. Upon starting study treatment, patients will receive open-label tozadenant at a dose of 120 mg BID. Adjustments to the open-label tozadenant dose are allowed to be made by the investigator starting at Week 2 and at any of the subsequent visits. Doses of 60 or 120 mg BID are permitted; the investigator may adjust a patient’s dose to either level as clinically indicated. The Interactive Response System (IXRS) will be used to assign, track and manage the tozadenant inventory at each study site.

The Schedule of Events/Evaluations for is shown below in [Table 1](#).

Table 1: Schedule of Events/Evaluations

Assessments	Study Period	Baseline	Open-Label Treatment						Safety	Early	Unscheduled
	Screening ^a	Predose	(52 weeks)						Follow-Up	Termination ^w	
	Study Week ^b	BL	2	6	12	24	36	52	56		
Study Visit	-6 to -1		(± 3 d)	(± 3 d)	(± 3 d)	(± 7 d)	(± 7 d)	(± 14 d) [16 weeks]	(28 ± 3 d after last dose of IMP)		
	V1	V2	V3	V4	V5	V6	V7	V8	V9		
Written Informed Consent	X										
Demographics and Medical History, including neurological and PD history	X										
Recording of concomitant and anti-PD medications	X	X	X	X	X	X	X	X	X	X	X
BP ^c , pulse ^c	X ^d	X ^d	X	X	X	X	X	X	X	X	X ^e
12-lead ECG ^f	X	X ^g	X	X	X	X	X	X	X	X	X ^e
Weight (include height at Screening)	X				X	X		X	X	X	X ^e
Physical and neurological examination	X				X	X	X	X	X	X	X ^e
PD diary training and diary concordance session	X										
Modified Hoehn and Yahr staging (observed ON; OFF estimated per history) ^h	X										
UPDRS Parts I, II, III and IV ⁱ	X	X	X	X	X	X	X	X		X	
MMSE-II (in ON state)	X										
mMIDI ^j	X		X	X	X	X	X	X	X	X	X ^e
ESS ^h		X	X	X	X	X	X	X	X	X	
PD diary collection (phone call prior to start of 3 consecutive 24 hour diary completion periods)	X ^k	X ^k			X ^l	X ^l		X ^l		X ^m	
PD diary review	X	X			X	X		X ^m		X ^m	
C-SSRS	X	X	X	X	X	X	X	X	X	X	X ^e
CGI-C ^h			X	X	X	X	X	X		X	
PGI-C ^h			X	X	X	X	X	X		X	
PDQ-39 ^h		X				X		X		X	
Sudden onset of sleep	X	X	X	X	X	X	X	X	X	X	
Fall questionnaire		X				X		X		X	
Healthcare Resource Utilization			X	X	X	X	X	X		X	
Nonmotor Symptom Questionnaire		X				X		X		X	
EQ-5D-5L ^h		X				X		X		X	
Recording of AEs	X ⁿ	X ⁿ	X	X	X	X	X	X	X	X	X

Assessments	Study Period	Screening ^a	Baseline Predose	Open-Label Treatment (52 weeks)						Safety Follow-Up	Early Termination ^w	Unscheduled
	Study Week ^b	-6 to -1	BL	2 (± 3 d)	6 (± 3 d)	12 (± 3 d)	24 (± 7 d)	36 (± 7 d)	52 (± 14 d) [16 weeks]	56 (28 ± 3 d after last dose of IMP)		
	Study Visit	V1	V2	V3	V4	V5	V6	V7	V8	V9		
Laboratory tests: hematology ^o , chemistry ^p (including thyroid function q)		X	X	X	X	X	X	X	X	X	X	X ^e
FSH test, females who are postmenopausal for < 2 years		X										
Method of contraception ^r		X	X	X	X	X	X	X	X	X	X	X ^e
Urine pregnancy test, females of childbearing potential ^s		X	X	X	X	X	X	X	X	X	X	X ^e
Urinalysis ^t		X	X	X	X	X	X	X	X	X	X	X ^e
Review of inclusion/exclusion criteria		X										
Final verification of eligibility			X									
Tozadenant blood sampling				X ^u								
IMP dispensing and/or return ^v			X	X	X	X	X	X	X		X	X ^e
eCRF completion		X	X	X	X	X	X	X	X	X	X	X

AE, adverse event; BP, blood pressure; CGI-C, Clinical Global Impression of Change; C-SSRS, Columbia-Suicide Severity Rating Scale; d, day; ECG, electrocardiogram; eCRF, electronic case report form; ESS, Epworth Sleepiness Scale; ET, Early Termination; FSH, follicle stimulating hormone; IMP, investigational medicinal product; mMIDI, Modified Minnesota Impulse Disorders Interview; MMSE-II, Mini-Mental State Exam – Second Edition (MMSE-II); PD, Parkinson’s disease; PDQ-39, Parkinson’s Disease Quality of Life Questionnaire; PGI-C, Patient’s Global Impression of Change; UPDRS, Unified Parkinson’s Disease Rating Scale; V, Visit.

Footnotes

^a Screening period may not exceed 6 weeks.

^b Visit windows for scheduled visits after Baseline (V2) are in relation to the date of the Baseline Visit (V2).

^c Obtain and record BP and pulse measurements after at least 5 minutes supine rest and again after standing for approximately 1 minute and 3 minutes.

^d At Screening and Baseline (before dosing), obtain and record serial BP and pulse measurements after at least 5 minutes supine rest and again after standing for approximately 1 and 3 minutes, on 3 occasions approximately 10 minutes apart.

^e Optional activities (e.g., additional assessments for evaluation of AEs) that may be performed at the investigator’s discretion.

^f A resting supine 12-lead ECG will be collected after the patient has been in a supine position for a minimum of 5 minutes. Ensure the ECG is collected when the patient is not experiencing dyskinesia that would interfere with an adequate recording.

^g At Baseline, obtain three 12-lead ECGs (i.e., 3 serial readings, performed several minutes apart). Ensure the ECGs are collected when the patient is not experiencing dyskinesia that would interfere with an adequate recording.

^h To be collected during patient’s ON state.

ⁱ UPDRS to be measured in ON state. UPDRS Part III should be measured approximately 1 to 3 hours after patients have taken a scheduled dose of levodopa (preferably their morning dose of levodopa). Patients will be instructed to have already taken their normally scheduled dose of levodopa and their IMP before arriving at the study site in order to have their UPDRS Part III evaluated in the ON state. UPDRS in the ON state will be measured at a time representative of the ON state in that patient, not in the patient’s “best” ON.

Table 1: Schedule of Events/Evaluations (continued)


^j At Screening, send patient for structured clinical interview if one or more positive mMIDI modules. If the structured clinical interview confirms that the subject does not have an ICD, he/she will not be considered ineligible on that basis. After Baseline, if patient has one or more positive modules on the mMIDI, their continued participation in the study should be discussed with the Medical Monitor.
 
^k The 3-day practice diary during the Screening Period and the 3-day Baseline diary must both be valid in order to randomize a patient. The trainer/rater will call the patient before the scheduled start of the diary completion periods to remind him or her to keep the PD diary and to review completion instructions. The patient will also be reminded to send the completed practice diary to the trainer/rater and to bring their Baseline diary to the Baseline Visit. If the practice or Baseline diary is invalid, the patient may be retrained and complete another practice or Baseline diary within the 6-week window of the Screening Period, if the patient is otherwise eligible for the study.
 
^l PD diary collected over the 3 consecutive 24-hour periods before the day of the scheduled study visits on Week 2, 6, 12, 18, 24, 36, and 52. The PD diary trainer/rater will call the patient before the scheduled start of the 3-day PD diary completion period (at the latest, on the last working day before the scheduled start of the PD diary completion) and review completion instructions. The patient will also be reminded to bring their PD diary to the visit. The trainer/rater will instruct the patient if the PD diary contains missing and/or invalid entries to reinforce instructions for appropriate completion.
 
^m Done only if the ET date coincides with the scheduled diary collection return date.
 
ⁿ Pretreatment AEs.
 
^o Hematology tests: Hemoglobin concentration, hematocrit, red blood cell count, total and differential white blood cell, thrombocyte (platelet) count.
 
^p Blood chemistry (including liver function) tests: Aspartate amino transferase (AST), alanine amino transferase, (ALT), gamma-glutamyl transpeptidase (GGT), alkaline phosphatase (ALP), lactate dehydrogenase (LDH), total bilirubin (conjugated and unconjugated), albumin, creatinine, urea/BUN, bicarbonate, uric acid, total protein, sodium, chloride, potassium, calcium, phosphate, glucose, cholesterol, creatine phosphokinase (CK).
 
^q TSH, free T₃, and free T₄.
 
^r For applicable patients: At Screening, document method of contraception used by patient. At subsequent visits, verify continuation of (or any change to) contraceptive method.
 
^s For females of childbearing potential: urine pregnancy test.
 
^t Urinalysis: Specific gravity, pH, ketones, blood, protein, glucose. If urine dipstick is positive for leukocytes, protein, or erythrocytes, a microscopic evaluation and culture will be performed.
 
^u A PK blood sample should be collected at the most convenient time during the Week 2 visit. Record the patient-reported date and approximate time when the patient took the most recent dose of IMP. Record the date and time of the PK sample collection. See Section 8.0 of the protocol. (Note: sites participating in Expanded PK Sampling should refer to Appendix 15.9.)
 
^v Patients will be instructed to take the assigned dose of open-label tozadenant by mouth BID, in the morning and in the evening preferably at the same time each day. The evening dose should be approximately 12 hours after the morning dose. Patients will be instructed to take their morning and evening doses at least 1 hour before or 2 hours after a meal and to refrain from eating for at least 1 hour after dosing.
 
^w If patient has discontinued IMP, perform Early Termination Visit as soon as possible after the last dose of IMP. If patient took the last dose of IMP 28 or more days prior to the Early Termination Visit, a Safety Follow-Up Visit (Section 6.2.16) is not required.

--

3.1. Analysis sets

3.1.1. Full Analysis Set (FAS)

The FAS will consist of all patients who are enrolled in the open-label phase 3 study.

3.1.2. Safety Set (SS)

The SS will consist of all enrolled patients who received at least one dose of IMP.

3.1.3. modified Full Analysis Set (mFAS)

The mFAS will consist of all enrolled patients who received at least one dose of IMP and who had at least one post-baseline visit.

3.1.4. Expanded PK Population (xPK)

The xPK Population will consist of all subjects with expanded PK and for whom there are adequate samples collected to provide analyzable PK data.

3.2. Sample Size Considerations

No formal sample size determination was performed for [TOZ-CL06](#). With an anticipated 30% screen failure rate, approximately 645 patients will be screened to enroll 450 patients.

3.3. Randomization

Not applicable since this is an open-label study where all patients start with 120mg.

4. STUDY VARIABLES AND COVARIATES

4.1. Safety Variables

Safety variables include the following:

- Treatment-emergent adverse events (TEAE).
- Physical and neurological examination.
- Supine and standing pulse and blood pressure.
- Standard 12-lead electrocardiogram (ECG): RR, PR, QRS, QT and QTcF.
- Laboratory parameters: hematology, chemistry, thyroid function (thyroid stimulating hormone [TSH], free T3, and free T4), and urinalysis.
- Columbia-Suicide Severity Rating Scale (C-SSRS).
- Daytime sleepiness as measured by the Epworth Sleepiness Scale (ESS)
- Assessment of sudden episodes of sleep.
- Modified Minnesota Impulsive Disorders Interview (mMIDI).

4.2. Other variables

Other variables include the following:

- Unified Parkinson's Disease Rating Scale (UPDRS) Part II (Activity of Daily Living (ADL) subscale) + Part III (motor subscale) total score.
- UPDRS Part II (ADL subscale) score.
- UPDRS Part III (motor subscale) score in the ON state.
- UPDRS Part I total score.
- UPDRS Part IV total score.
- Dyskinesia as measured by questions 32, 33 and 34 of UPDRS Part IV.
- Motor fluctuations as measured by question 39 of UPDRS Part IV.
- Clinical Global Impression of Improvement (CGI-I).
- Patient's Global Impression of Improvement (PGI-I).
- Parkinson's Disease Quality of Life Questionnaire (PDQ-39; total score and individual domain scores).
- Non-motor Symptom Questionnaire.
- EuroQol 5D-5L Health Questionnaire (EQ-5D-5L).
- Patient-completed diaries (number of hours per day spent as follows: OFF, ON time without troublesome dyskinesia, total ON time, ON time with troublesome dyskinesia and asleep time).
- Healthcare Resource Utilization
- Fall Questionnaire

4.3. Pharmacokinetic Variables

- Tozadenant PK concentrations at Week 2 and PK concentration and PK parameters c_{max} , t_{max} , and AUC_{0-last} for expanded PK.

4.4. Predetermined Covariates and Prognostic Factors

Not applicable as exploratory analyses will be documented by descriptive statistics.

5. DEFINITIONS

5.1. Treatment Group Labels

The following treatment group label will be used in the TFLs:

- Tozadenant

5.2. Age

The following SAS[®] code is used to calculate subject age (years):

$$\text{Age} = \text{floor}(\text{intck}(\text{'month'}, \text{birth date}, \text{IC date}) - (\text{day}(\text{IC date}) < \text{day}(\text{birth date}))) / 12,$$

Where intck is a SAS[®] function counting integer days between birth date and informed consent date.

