4.0 SELECTION AND WITHDRAWAL OF PATIENTS

4.1 Inclusion Criteria

Patients must fulfill all of the following inclusion criteria in order to be included in the study:

1. Patient is informed and given ample time and opportunity to think about his/her participation in this study and has given his/her written informed consent on an Independent Ethics Committee (IEC) or Institutional Review Board (IRB) approved consent form.
2. Patient is considered reliable and capable of adhering to the protocol (e.g., able to understand and complete diaries), visit schedule, and medication administration instructions according to the judgment of the investigator.
3. Patient has a documented history of idiopathic Parkinson's disease consistent with the UK Parkinson's Disease Society Brain Bank Diagnostic criteria prior to the Screening Visit.
4. Patient has a PD duration of at least 3 years from diagnosis.
5. Patient has a modified Hoehn and Yahr stage 2–4 when in OFF state (estimated) and ≤ 3 in ON state.
6. Patient is male or female and 30–80 years old (inclusive) at Screening.
7. Patient must have a good response to levodopa in the opinion of the investigator, be taking at least four doses of a levodopa-containing medication per day, and at least one other concomitant anti-PD medication (dopamine agonists, MAO-B inhibitors, anticholinergic agents, amantadine or entacapone).
8. Patient is maintained on a regimen of permitted anti-PD medications that has been stable for at least 4 weeks prior to Screening.
9. Patients must have been taking a levodopa-containing anti-PD medication continuously for at least the previous 12 months and must be currently experiencing end-of-dose “wearing-off” with at least 2.5 hours of OFF time per day as confirmed by a 3-day Baseline diary.

10. Patient must have achieved the following results for PD diary training, practice diary collection, and Baseline diary recordings:

- a. During a diary concordance session with an approved PD diary trainer/rater (minimum 2.5 hours), patient achieved at least 80% overall diary concordance including at least 1 OFF interval.
- b. Returned a valid 3-day (i.e., 3 consecutive 24-hour periods) practice diary.
- c. Returned valid diary recordings for each of the 3 consecutive days preceding the Baseline Visit that indicated at least 2.5 hours of OFF time on each of the 3 days.

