12.3 Patient Privacy

Sponsor staff (or designee) will affirm and uphold the patient's confidentiality. Sponsor staff (or designee) will affirm that the patient's date of birth and initials will not be collected in the European Union (EU) or other regions where it is not permitted. Throughout this study, all data forwarded to the Sponsor/Sponsor's designee will be identified only by the patient number and/or site identifier (ID) and patient screening number.

The investigator agrees that representatives of Sponsor, its designee, representatives of the relevant IRB/IEC, or representatives of regulatory authorities will be allowed to review that portion of the patient's primary medical records that directly concerns this study (including, but not limited to, laboratory test result reports, ECG reports, admission/discharge summaries for hospital admissions occurring during a patient's study participation, and autopsy reports for deaths occurring during the study).

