9.4. Demographic and Baseline Characteristics

Demographic and baseline characteristics will be summarized descriptively in the FAS. These variables include:

- Gender
- Race and ethnicity
- Age (years)

- Body weight (kg)
- Height (cm)
- Body Mass Index (BMI) (kg/m²)
- Duration of PD (years)
- Hoehn and Yahr Staging of PD in ON state and OFF state (best estimate)

Age will also be classified into 3 categories (≥ 30 to 54, ≥ 55 to 68 and ≥ 69 to 80 years).

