Source Listing: Listing *X* (*data set name*)
SOURCE PROGRAM: path\filename
6. All data listings should be sorted by investigator site, patient within investigator site, and study visit date/time within patient where appropriate.
7. For tables that summarize categorical (discrete) data, all categories between the maximum and minimum category should be presented in the table, even if there is zero

entry for a particular category. An Unknown or Missing category should be added to any variables to indicate missing information, if appropriate

Severity Rating	n
Severe	0
Moderate	8
Mild	3
Missing	2

8. If the categories are not ordered (e.g., Medical History, Reasons for Discontinuation from the Study, etc.), then only those categories for which there is at least 1 patient represented in 1 or more groups should be included.
9. Unless specified otherwise, tabular display of data for medical history, prior / concomitant medications, and all tabular displays of adverse event data should be presented by the body system, drug class, or SOC with the highest occurrence in decreasing order. Within the body system, drug class and SOC, medical history (by preferred term), drugs (by ATC1 code), and adverse events (by preferred term) should be displayed in decreasing order. If incidence for more than 1 term is identical, they should then be sorted alphabetically. Specifically, prior and concomitant medications other than Anti-Parkinson's medications should be displayed by therapeutic class and preferred term. Prior and concomitant Anti-Parkinson's medications should be displayed by therapeutic class, chemical/therapeutic/pharmacological subgroup, and preferred term.
10. Unless otherwise specified, the estimated mean and median for a set of values should be printed out to one more decimal place than the original values and rounded appropriately. Standard errors (or standard deviations) should be printed out to two additional decimal places than the original values and rounded appropriately. The range should report the same as the original values. For example, for age (with original value in whole years):

N	xx
Mean	xx.x
S.E.	xx.xx
Median	xx.x
Range	xx-yy

11. All fractional numeric values should be printed with a zero to the left of the decimal point (e.g., 0.12, 0.3).

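### The age formula in SAP 5.2 applies floor() before dividing by 12, so it returns twelfths of a year rather than whole years, and it names no age source where birth date is not collected

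*SAP*

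**What the plan says.** SAP 5.2 gives SAS code for age in years. With B for birth date and C for consent date, its structure is `floor(intck('month', B, C) - (day(C) < day(B))) / 12`. The sentence below the code describes intck as a function "counting integer days between birth date and informed consent date".

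Three other places bear on what the result should look like:

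- SAP 9.4: "Age will also be classified into 3 categories (≥ 30 to 54, ≥ 55 to 68 and ≥ 69 to 80 years".
- SAP 11.1 item 10 sets out its layout example "for age (with original value in whole years", with the range shown as two integers.
- Protocol 4.1, criterion 6, admits patients "30–80 years old (inclusive) at Screening".

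On the input, Protocol 12.3 states that the patient's "date of birth and initials will not be collected in the European Union (EU) or other regions where it is not permitted". Europe is one of the planned regions (Protocol 3.1.3). SAP 5.2 gives no alternative derivation, and SAP 9 says that missing data will not be imputed.

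**The concern.** The adjusted month count is an integer before floor() is applied, so floor() has no effect and the division by 12 produces fractions. Bands whose limits are 54 then 55, and 68 then 69, leave no gap only if age is in whole years. A programmer who copies the code therefore gets values the banding rule does not cover. A programmer who follows the sentence about days gets something that is not an age at all.

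Separately, the code needs the day, month and year of birth. Where these are not collected, it has nothing to work on and the SAP names no substitute.

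At stake are the age summary and the age-band rows of the demographic table, and agreement between two programmers working from a specification whose code, text and bands disagree.

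**Working it through.** **Bracket check.** In the printed formula the brackets balance, and the one opened by floor closes immediately before `/ 12`. The division is outside floor().

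**Worked dates (illustrative).**

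- Born 10 Mar 1962, consent 20 Feb 2017. Months = (2017 − 1962) × 12 + (2 − 3) − 0 = 659. The last term is 0 because day 20 is not before day 10. As written: 659 / 12 = 54.92. With the division inside: floor(54.92) = 54.
- Born 1 Sep 1936, same consent date. Months = (2017 − 1936) × 12 + (2 − 9) = 965. As written: 80.42. With the division inside: 80. This patient meets the 30–80 criterion but lies above a band that stops at 80.0.
- First patient again, counting days as the text says: 20,071 / 12 is about 1,673.

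**Share of non-integer ages.** The result is an integer only when completed months are a multiple of 12. If birthdays are evenly spread, 1/12 are integers and 11/12 (about 91.7%) are not.

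**Shift in the mean.** Months beyond the last birthday then run evenly over 0 to 11, with mean 5.5. The excess over completed years is 5.5 / 12 = 11/24, about 0.46 year.

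**Share in no band.** This applies only if the bands are coded as closed at 54.0, 68.0 and 80.0. The uncovered values are those strictly between 54 and 55, 68 and 69, and 80 and 81. Neither document gives an age distribution, so one must be assumed. For ages uniform on 30 to just under 81:

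3 × (11/12) / 51 = 2.75 / 51 = 5.4%.

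For normal ages truncated to the same range, with mean 58–68 and SD 7–11, simulation (1,000,000 ages per scenario) gives:

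| Assumed mean, SD | Share in no band |
|---|---|
| 58, 11 (lowest) | 5.8% |
| 64, 9 | 6.9% (54–55: 2.4%; 68–69: 3.7%; 80–81: 0.8%) |
| 68, 10 (highest) | 7.6% |

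The overall range is about 5% to 8% of patients who have a birth date. The documents do not say how many of the planned 450 that is.

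**After the correction.** With floor() applied after the division, the share of eligible patients outside the bands is 0% in every scenario. Patients with no birth date are not helped by moving the bracket.

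**The case against.** **The intent is plain.** SAP 9.4 and 11.1 read together show that whole years are meant. A programmer who codes the bands as below 55, below 69 and below 81 loses nobody, even with fractional ages. SAP 10 requires independent programming of every unique table, which might catch the slip. This stands as a limit on the consequence: patients drop out of the bands only under a literal reading of their limits. It does not repair 5.2, because the SAP nowhere states the half-open limits, and two programmers can copy the same line.

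**The formula was read from a PDF.** A single lost bracket would leave the brackets unbalanced, and they balance. A matched pair would have to be missing. This is unlikely, but worth a glance at the signed SAP.

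**Missing ages are provided for.** SAP 11.1 items 7 and 12 allow a Missing category and base percentages on patients with an observation. That handles an absent age openly. It does not handle a non-missing value such as 54.92.

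**EU patients do have an age.** A reader might infer that European patients will have no age in the analysis. The documents do not support that. Protocol 12.3 rules out date of birth, not age. Demographics are taken at Screening, eligibility by age has to be checked, and both the ESS form and the non-motor scale carry an age field. What stands is narrower: the printed formula returns nothing for these patients, and the SAP does not say what replaces it.

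**Conclusion.** The code in SAP 5.2 is wrong as written and contradicts the SAP's own whole-year bands and formatting rule. The sentence about days contradicts the code. These two findings rest on the printed text alone.

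The consequences are conditional. The 11-in-12 share and the 0.46-year shift assume evenly spread birthdays. The 5–8% in no band assumes an age distribution that the documents do not give, closed band limits, and a birth date on record. A reader might go on to infer that about 7% of all 450 patients drop out of the age table. That is not supported: the figure depends on the assumed distribution and on literal coding of the bands, and it cannot cover patients for whom the formula yields no age in the first place.

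The matter is minor. SAP 4.4 uses no covariates, SAP 9 plans no formal tests, and the safety analyses in SAP 9.8 do not use age. The effect is confined to descriptive demographics.

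**What to change.** 1. Replace the line with `Age = floor((intck('month', birth date, IC date) - (day(IC date) < day(birth date))) / 12)`.
2. Change 'days' to 'months' in the sentence below it.
3. Add one sentence naming the age source where birth date is not collected, for example age or year of birth recorded at Screening. First confirm that the eCRF captures it, since the documents do not show this.

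The cost is one corrected line, one word and one sentence in the SAP. No new data collection is needed if the eCRF already holds an age or year of birth.
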